8. ANALYSIS AND STATISTICS

8.1 Power Calculations and Sample Size

The primary outcome measure is the percentage of patients in each arm that had a lipid panel checked or initiated LLT. Assuming 80% of the subjects in the intervention group have their lipids checked within the 3 months of the study, and 60% of the subjects in the control group have their lipid checked N=64 subjects per group would have at least 80% power to detect a margin difference of 20%, for a one-sided test and significance level of 0.05. We recognize that the sample of 128 subjects is modest, which reflects the pilot nature of the study in the context of a training grant. We will use data from this pilot study to design a more definitive trial powered to detect smaller differences in the primary outcome, and to compare usual care with the intervention.

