3. STUDY OBJECTIVES AND OUTCOMES

3.1 Primary Objective

The primary objective is to test the difference in the proportion of subjects who receive cardiovascular risk assessment or learning from their healthcare provider that they already had one in the past year, between subjects randomized to the peer coaching condition and subjects randomized to the self-administered online learning condition.

3.2 Secondary objectives:

To determine whether the CARE RA program is effective in improving the following patient generated health data compared to subjects in the self-administered online learning arm.

1. Change in Routine Assessment of Patient Index Data (RAPID3) score from baseline to the end of the study between arms.
2. Change in Social Support Survey Score from baseline to the end of the study between arms.
3. Change in Patient Activation Measure (PAM) score from baseline to the end of the study between arms.
4. Change in Patient Health Questionnaire – 8 (PHQ-8) score from baseline to the end of the study between arms. Subjects who score a 10 or higher on the PHQ-8 at baseline data collection will be referred to mental health resources and counseling (websites, links, educational materials) by the study team. Peer coaches will be trained to direct subjects who express depressed thoughts and feelings during the course of the program to the mental health resources and counseling and will report such instances to the research team.
5. Change in General Self-Efficacy (GSF) score from baseline to the end of the study between arms.
6. Change in Medication Understanding and Use Self-Efficacy Scale (MUSE) score from baseline to the end of the study between arms.
7. We will examine the feasibility of the intervention by having 80% or more of the subjects complete the intervention.

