5.3 Planned number of subjects

We plan to enroll 128 subjects into this study. We will recruit patients from the ArthritisPower Patient Powered Research Network (PPRN), the Bendcare patient network, [name] practice at New York Presbyterian – Brooklyn, and social media using Twitter. We will also be recruiting participants using flyers created by a company (BuildClinical). These flyers will be posted online and interested participants will be referred to us. The PPRN has over 28,000 patients with arthritis throughout the United States and territories. In order to enroll this number of subjects, it is expected that approximately 180 subjects will be screened. This takes into account an estimate of at least a 20% screen failure rate between Screening and Baseline. We will monitor the actual screen failure rate to make estimates for the planned larger study to follow this one.

- First subject's first enrollment: Q1 2021
- Last subject's last encounter/call: Q2 2022

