7. STUDY PROCEDURES AND SCHEDULE

7.1 Intervention fidelity measures

A careful assessment of intervention implementation can provide insights into which aspects of the intervention were particularly effective. We will use several strategies to monitor intervention fidelity.

First, we will ask peer coaches to use Zoom teleconference calls for intervention delivery and record the weekly sessions between peer coaches and subjects. The goal of these recordings is to monitor fidelity of the intervention and monitor duration of the calls. These secure calls will be recorded and stored in the secure and HIPAA compliant server of the WCM Division of GIM. Study staff will review each session and use a checklist to assess intervention fidelity for each session.

Second, the peer coaches will have a checklist that they will have to complete as they go through the call of all the activities and topics that they have to cover in each session, which will ensure that these are completed by the end of each call. We will collect these checklists and compare the self-assessment of the coach to those of the study team based on their review of the Zoom call recordings. In the future larger trial, we will use these comparisons to plan for how to monitor intervention fidelity.

Third, we will monitor intervention implementation on an ongoing basis through weekly teleconferences with peer coaches, and weekly outreach to each peer coach individually throughout the intervention period. We will provide updates on the progress of the study, collaboratively troubleshoot problems, and provide ongoing advice, which often stems from other peers. At these calls, coaches will be asked to report on their clients and progress, giving the opportunity to reinforce the study protocol and MI skills.

Fourth, the research team will contact each subject twice over the 5-week intervention period to check on how the intervention is unfolding from the subject perspective.

7.2 Data collection:

All subjects will receive a baseline telephone call, the post-intervention follow up call, and the 3-month/final follow up call from the study team (Table 2). Subjects who are lost to follow-up or drop out of the study before completion will be contacted to complete the program evaluation portions of the intervention.

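### The 64 per group behind the power claim in 8.1 is essentially the minimum number with an outcome, yet exactly 128 are enrolled, with no allowance for missing outcomes

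*Combined protocol and SAP*

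**What the plan says.** Section 8.1 sets the assumption for the peer coach arm ("Assuming 80% of the subjects in the intervention group have their lipids checked within the 3 months of the study") and, for the online learning arm, a lower rate ("60% of the subjects in the control group have their lipid checked"). It concludes that "N=64 subjects per group would have at least 80% power to detect a margin difference of 20" percentage points; the calculation is stated "for a one-sided test and significance level of 0.05". It adds that the sample is modest because this is a pilot on a training grant.

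Section 5.3 takes the same number as the enrolment target: "We plan to enroll 128 subjects into this study". About 180 people are to be screened, and the reason given is: "This takes into account an estimate of at least a 20% screen failure rate between Screening and Baseline". Section 5.4 keeps recruitment open until 128 are recruited.

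Loss after enrolment is foreseen but not quantified. Section 7.2 says "Subjects who are lost to follow-up or drop out of the study before completion will be contacted", for the program evaluation only. In Table 2 the column for lost or dropped-out subjects is marked for the evaluation survey and the focus group or interview, and is blank for the cholesterol test. Table 4 asks what the attrition rate was and how it affected the conclusions on effectiveness. Section 8.2 analyses by intention-to-treat and gives no rule for a missing primary outcome. It also specifies two-sided testing at 0.05, in contrast to 8.1.

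**The concern.** A sample size formula returns the number of subjects who contribute an outcome. Here that number and the number enrolled are the same, so the power statement is accurate only if nearly every enrolled subject supplies a primary outcome. The one allowance in the plan, for screen failure, protects the enrolment count and does nothing for outcome data.

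At stake is how the result is read. If power is lower than stated, a null result will look more informative than it is. Section 8.1 also says that the pilot will inform a definitive trial, and its sizing needs enrolled and evaluable numbers kept apart.

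**Working it through.** **Inputs.** From 8.1: p1 = 0.80, p2 = 0.60, difference 0.20, one-sided alpha 0.05 (z = 1.645), power 80% (z = 0.842), 64 per group. From 5.3: 128 enrolled, which is 64 per group assuming equal allocation. From 8.2: two-sided alpha 0.05 (z = 1.960). Loss rates of 5%, 10% and 20% are assumptions of this review.

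**Step 1: reproduce the plan's figure.** The mean rate is 0.70, so the null variance term is 2 × 0.70 × 0.30 = 0.42. The alternative variance term is 0.80 × 0.20 + 0.60 × 0.40 = 0.40.

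- Pooled: n = [1.645 × √0.42 + 0.842 × √0.40]² / 0.20² = 63.9, so 64 per group.
- Unpooled: n = 0.40 × (1.645 + 0.842)² / 0.20² = 61.8, so 62 per group.

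Section 8.1 does not name its formula; the pooled one returns 64.

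**Step 2: power at 64 per group, no loss.** Pooled power = Φ{[0.20 × √n − z × √0.42] / √0.40}.

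- One-sided: [0.20 × 8 − 1.645 × 0.648] / 0.632 = 0.844, so power is 80.1%. The unpooled formula gives 81.2%.
- Two-sided: [1.600 − 1.960 × 0.648] / 0.632 = 0.52, so power is 69.9%; 82 per group would be needed for 80%.

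The two-sided figures use the z approximation for two proportions. Section 8.2 names t-tests.

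**Step 3: how much reserve there is.** By the pooled formula, one subject lost in total gives 79.8%, and one lost in each group (63) gives 79.5%. By the unpooled formula the reserve is 64 − 62 = 2 per group.

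**Step 4: power with missing outcomes.** Assume loss is equal in both arms, unrelated to the outcome, and missing subjects are left out. Then n = 64 × (1 − d), and the pooled formula gives:

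| Assumed loss d | Evaluable per group | One-sided 0.05 (8.1) | Two-sided 0.05 (8.2) |
|---|---|---|---|
| 0% | 64 | 80.1% | 69.9% |
| 5% | 60.8 | 78.2% | 67.6% |
| 10% | 57.6 | 76.3% | 65.2% |
| 20% | 51.2 | 71.8% | 60.0% |

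**Step 5: enrolment that would keep 64 evaluable, for scale only.** 64 / (1 − d), rounded up, is 68 per group (136) at 5%, 72 (144) at 10% and 80 (160) at 20%.

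**The case against.** The strongest reply is that drop-out is not the same as a missing outcome. Section 8.2 counts a lipid check found through a national laboratory chain as well as one reported by the subject, so a person who stops answering may still have an outcome. Section 7.2 adds telephone follow-up of incomplete surveys, and 8.2 commits to retaining subjects. This stands in part: true loss may well be smaller than drop-out. It does not remove the point, because no procedure obtains laboratory records for every subject, and a test done elsewhere would be known only by report. Intention-to-treat says who is analysed; it does not supply a missing value.

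A second reply is that about 180 screened, at exactly 20% failure, leaves 180 × 0.80 = 144 people, which might look like a hidden reserve. It is not, because recruitment ends at 128.

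A third is that this is a pilot that admits a modest sample, and that measuring attrition is a proper aim of a pilot. That is fair, and it limits the consequence. It does not make the power statement accurate. Covariate adjustment in 8.2 might recover some power, but the plan does not quantify this.

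Several stronger readings are tempting and are not supported:

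- *The plan expects 20% loss.* The feasibility goal is "having 80% or more of the subjects complete the intervention" (section 3.2). That concerns completing the program, not ascertaining the outcome, and 8.2 analyses subjects whether or not they complete it. No drop-out rate is given anywhere; 20% is only an upper illustration.
- *The claim fails as soon as one outcome is missing.* This is true of the pooled formula, but the unpooled one tolerates 2 losses per group.
- *Power falls to about 68% at 10% loss or 57% at 20%.* These one-sided figures arise if missing is scored as not tested (72% vs 54%, or 64% vs 48%, with 64 per group). The plan states no such rule.

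**Conclusion.** The point holds, at moderate size. The 64 per group in 8.1 is essentially the minimum evaluable number, and it is also the enrolment target, so at least 80% power is not what 128 enrolled subjects deliver once more than a trivial number of outcomes is missing. On the plan's own one-sided test the shortfall is about 2 points at 5% loss, 4 at 10% and 8 at 20%. These figures rest on assumed loss rates, equal loss in both arms, loss unrelated to the outcome, and the rates of 80% and 60% in 8.1.

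The one- versus two-sided conflict between 8.1 and 8.2 is a separate matter and costs more: about 10 points even with complete data. The two add up, so 20% loss on a two-sided test leaves about 60%. Fixing either one leaves the other in place. A reader might infer that the trial must be enlarged. The documents do not require that of a pilot; they require an accurate statement of its power.

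**What to change.** Keep 128. In section 8.1, say that 64 per group is the number with a primary outcome, and replace the claim of at least 80% with the power at assumed missing-outcome rates of 5%, 10% and 20%, labelled as assumptions.

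First reconcile 8.1 and 8.2 to one test, and compute the figures on that test: about 78%, 76% and 72% if one-sided, or about 68%, 65% and 60% if two-sided (about 70% with no loss). One-sided figures should not be inserted while 8.2 still tests two-sided.

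The cost is one or two sentences and a less favourable stated power. Enrolment need not change.

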5.4 Recruitment

Figure 2 outlines the workflow of this study from recruitment to final data collection.

Recruitment

We will send out invitations to participate in CARE RA to members of the ArthritisPower registry and the Bendcare patient network via email messages in several waves. We will send out 200-400 invitations at a time and continue to send out invitations based on the response and on peer coach capacity. Bendcare will also reach out to their patients to determine their interest in this study. Bendcare will screen patients for eligibility. Eligible patients will be consented by Bendcare and transferred to the research team for randomization. Bendcare will provide access to this REDCap database used to screen and consent Bendcare patients to the WCM research team within their secure network. We will also be recruiting participants using flyers created by a company (BuildClinical). These flyers will be posted online and interested participants will be referred to us. If the patient clicks on the online flyer, they'll be prompted to complete the BuildClinical screening survey based on our eligibility criteria.

We will post a recruitment video on Twitter through the PI's professional account. The recruitment video will briefly detail the CARE RA study and invite people to fill out an interest survey through REDCap if they would like to be contacted by the research team for more information. Once an individual completes the interest survey, the research team will reach out to them.

We will further increase recruitment through the patient list of [name], [name], [name], [name], [name], and [name]. All physicians have provided our team with authorization to contact their patients whom our team will identify using EPIC. To help streamline the process of identifying patients, we will use the EHR Data and Reporting system TRAC to extrapolate patients that meet the eligibility criteria. We will not reach out to patients who marked in EPIC their wish not to be contacted for research. We will reach out to patients through doximity.

Once a person consented to participate in the study, all data collected will follow those stipulated by the study. These recruitment processes will be in place until 128 subjects are recruited.

Screening

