8.2 Data Analysis

To analyze the data, descriptive analyses (means, medians, standard deviations, proportions, and frequency distributions) and correlation analyses (Spearman/Pearson rank correlations) will be conducted to assess and describe the cohort. Baseline comparability between study arms will be assessed with parametric and nonparametric analyses including two sample t-tests, Wilcoxon Rank Sum, and Chi-Square tests of proportions. Every effort will be made to keep subjects in the study for the entire follow-up. Analysis will be based on intention-to-treat, regardless of whether the subject completed the intervention program. The primary outcome is the percentage of patients with lipids checked (available now through national laboratory chain) or that reported having their lipids checked. Secondary outcomes include the percentage of subjects that reported initiating LLT, self-efficacy, and patient activation as described above. We will determine these outcomes in each group (self-administered online learning program and the CARE RA arm) as well as differences in these outcomes between the groups. Two-sided t-tests will be used to calculate differences and P values ≤ 0.05 will be considered statistically significant. We will examine differences in socio-demographics, disease severity, and depressive symptoms. These characteristics will be included in a multivariable logistic regression model to determine their association with the outcome (lipids being checked) and potentially increase the statistical power of the test of group differences.

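### The 80% power in section 8.1 belongs to a one-sided 0.05 test; the two-sided 0.05 test in section 8.2 has about 70% (unadjusted, complete outcomes)

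*Combined protocol and SAP*

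**What the plan says.** Section 8.1 (Power Calculations and Sample Size) sets the design alternative. The intervention rate is given as "Assuming 80% of the subjects in the intervention group have their lipids checked within the 3 months of the study", and the control rate is 60%. It concludes that 64 subjects per group give "at least 80% power to detect a margin difference of 20%, for a one-sided test and significance level of 0.05".

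Section 8.2 (Data Analysis) names the primary outcome (lipids checked) and the secondary outcomes, and says that both will be compared between the arms. It then gives one rule for all of them: "Two-sided t-tests will be used to calculate differences and P values ≤ 0.05 will be considered statistically significant". No one-sided test appears in 8.2. The section also plans a multivariable logistic regression for lipids being checked, which may "potentially increase the statistical power of the test of group differences". It gives no figure for that gain and does not name the model as the primary test.

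On numbers enrolled, section 5.3 plans 128 subjects from about 180 screened and explains the difference this way: "This takes into account an estimate of at least a 20% screen failure rate between Screening and Baseline". Section 5.4 gives the stopping point for enrolment: "These recruitment processes will be in place until 128 subjects are recruited".

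**The concern.** A power figure means something only for the test that will be run. A one-sided 0.05 test needs a z statistic of 1.645 in the favourable direction; a two-sided 0.05 test needs 1.960. Section 8.1 uses the first threshold and section 8.2 the second, without explanation.

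Two things are at stake:

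- **The power is overstated.** A non-significant primary result would be read as coming from a trial with a 20% chance of missing the assumed effect, when that chance is nearer 30%. The pilot is meant to inform a larger trial, so this reading matters.
- **The decision rule can be disputed.** On a plain reading 8.2 governs the analysis. But the unexplained one-sided statement in 8.1 gives room to call a favourable two-sided P between 0.05 and 0.10 significant after the data are seen.

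**Working it through.** **Inputs.** p1 = 0.80, p2 = 0.60, n = 64 per arm, one-sided alpha 0.05 (section 8.1); two-sided alpha 0.05 (section 8.2); total 128 = 2 × 64 (sections 5.3 and 5.4). Mean rate = 0.70.

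**Formulas (pooled normal approximation, no continuity correction).**

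- A = sqrt(2 × 0.70 × 0.30) = sqrt(0.42) = 0.6481
- B = sqrt(0.80 × 0.20 + 0.60 × 0.40) = sqrt(0.40) = 0.6325
- n per arm = (z_alpha × A + 0.8416 × B)² / 0.20²
- power = Φ[(0.20 × sqrt(n) − z_alpha × A) / B]

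**Step 1: reproduce section 8.1 (one-sided, z = 1.645).**

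- n = (1.0660 + 0.5323)² / 0.04 = 63.9, so 64 per arm.
- Power at 64 = Φ[(1.600 − 1.066) / 0.6325] = Φ(0.844) = 80.1%.

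The stated figure is correct for a one-sided test.

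**Step 2: the test in section 8.2 (two-sided, z = 1.960).**

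- Power at 64 = Φ[(1.600 − 1.270) / 0.6325] = Φ(0.521) = 69.9%.
- n for 80% power = (1.2702 + 0.5323)² / 0.04 = 81.2, so 82 per arm (164 in total).
- With 64 per arm, 80% two-sided power needs p1 of about 82.2% against 60%.

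**Step 3: does the choice of method matter?** Power at 64 per arm:

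| Method | One-sided 0.05 | Two-sided 0.05 |
|---|---|---|
| Pooled z | 80.1% | 69.9% |
| Unpooled z | 81.2% | 71.6% |
| Arcsine | 80.4% | 70.6% |
| z-test, exact binomial enumeration | 80.7% | 70.7% |
| t-test on 0/1 data, exact enumeration | 80.5% | 70.7% |
| Continuity-corrected z | 74.1% | 62.7% |
| Fisher's exact test, exact enumeration | 75.1% | 63.0% |

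None of these methods reaches 80% two-sided. The t-test row is the test 8.2 literally names. The unpooled formula needs 79 per arm for 80% two-sided power.

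**Step 4: how often do the two rules disagree?** At 80% vs 60%, the exact probability of passing the one-sided rule and failing the two-sided one is 80.66% − 70.73% = 9.9% for the z-test (9.8% for the t-test).

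Example: 48/64 (75.0%) vs 38/64 (59.4%). The difference is 0.15625 and the pooled rate is 86/128 = 0.6719. SE = sqrt(0.6719 × 0.3281 × 2/64) = 0.0830, so z = 1.882. One-sided P = 0.030; two-sided P = 0.060.

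**Step 5: missing outcomes (rates assumed here; the plan gives none).** Two-sided pooled power:

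| Assumed missing | Complete cases only | Missing counted as not checked |
|---|---|---|
| 10% | n = 57.6: 65.2% | 72% vs 54%, n = 64: 56.0% |
| 20% | n = 51.2: 60.0% | 64% vs 48%, n = 64: 44.5% |

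**The case against.** The strongest defence is that this is a pilot. Section 8.1 itself calls the sample modest, ties it to a training grant and leaves smaller differences to a later trial. Section 8.2 reads as the governing rule, its type I error is not inflated, and on that reading the defect is a single misstated figure. All of that is fair, and it limits the practical consequences. It does not reconcile the sections: the plan still makes a numerical power claim for a formal primary comparison, and that claim is for a different test.

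A second point is that 70% describes only one candidate analysis. The logistic model is the only method tied by name to lipids being checked, and covariate adjustment might recover some power. The gain cannot be computed from the documents, so the 70% is limited to the unadjusted comparison. The model does not rescue the 80% either, because it has no one-sided rule and 8.1 does not rely on it.

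It could also be said that the two-sided sentence is meant only for the continuous scores. The text does not say so; it follows directly on the sentence covering primary and secondary outcomes together.

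Finally, missing data may be lighter than the illustrations in the working. Blinded telephone follow-up (section 7.2) and laboratory-chain results or self-report (section 8.2) could fill gaps. That stands: those rows are illustrations, and the finding does not depend on them.

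**Conclusion.** The concern holds. Sections 8.1 and 8.2 use different tests, and nothing elsewhere in the document reconciles them. For 80% vs 60% with 64 per arm and complete outcomes, the unadjusted two-sided 0.05 comparison has about 70% power (69.9% to 71.6% across the uncorrected methods, about 63% with a continuity correction or Fisher's exact test), against the 80% claimed. The shortfall is about 10 percentage points.

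Enrolment stops at exactly 2 × 64, and the only allowance described is for screen failure before baseline. Any missing outcome therefore lowers power further, by an amount the documents do not allow one to state. Because the mismatch touches both the primary decision rule and the headline power claim, it should be corrected before data are seen.

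**What to change.** Keep 128 subjects and the two-sided test in section 8.2. Restate section 8.1 along these lines: *64 per arm gives about 70% power (two-sided 0.05, unadjusted comparison, complete outcomes) for 80% vs 60%, or 80% power for about 82% vs 60%.*

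If a one-sided primary test is truly intended, pre-specify it in 8.2 for the primary outcome, before data are seen, and leave the 8.1 figure as it is.

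If 8.1 is to show power under missing outcomes, label the rate as an assumption and state how missing outcomes are handled.

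The cost is wording only: no extra patients and no change in conduct. Under the first option the stated power becomes less favourable.
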